3.3.2 Participant Exclusion

- Missing data > 10% of required outcome measures.
- Severe violation of the study protocol.

3.3.3 Early Study Termination

- Incidence of serious adverse events (SAEs) > 10%.
- No clinically meaningful differences in the primary outcome measure identified by the Data Monitoring Committee.
- Uncontrollable study bias or operational difficulties.

4. Intervention Measures

4.1 Intervention Product

Amino Acid (15) Peritoneal Dialysis Solution (2 L/bag, manufactured by Shandong Weigao Group).

4.2 Administration Protocol

- Participants maintain their original peritoneal dialysis regimen throughout the study.
- Replace one bag of conventional glucose-based dialysis solution with Amino Acid (15) Peritoneal Dialysis Solution after lunch, once daily.
- Continuous intervention for 6 months per participant.
- Dose adjustment: The 2 L/dose is maintained unless safety issues arise (e.g., severe metabolic acidosis), which will be managed with oral sodium bicarbonate as clinically indicated.

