5.1 Primary Outcome Measure

Serum albumin (Alb) level: Measured at baseline (enrollment day), 3 months, and 6 months post-intervention.

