5.3 Safety Outcome Measures

- Adverse events (AEs): Including peritonitis, gastrointestinal reactions (e.g., abdominal distension, diarrhea), metabolic acidosis, etc.; recorded throughout the study period.
- Serious adverse events (SAEs): Including death, life-threatening events, prolonged hospitalization, permanent disability, etc.; reported to the Ethics Committee and sponsor within 24 hours of identification.

6. Study Procedures

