6.1 Timeline

Phase	Duration	Key Activities
Preparation & Rolling Recruitment	January 2026 – June 2027 (18 months)	Screen participants, verify eligibility, obtain informed consent, complete baseline assessments (recruitment continues until 6 months before study end to ensure all participants finish 6-month follow-up)
Intervention & Follow-up (Per Participant)	6 Months Post-Enrollment	Implement intervention, conduct biweekly follow-up (record UF and AEs), perform 3-month serum albumin testing
Final Post-Intervention & Study Closure	July 2027 – December 31, 2027 (6 months)	Complete 6-month outcome assessments for the last enrolled participants; finalize data verification, statistical analysis, and study report writing

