6.2 Specific Procedures

- Baseline Assessment (Enrollment Day):** Collect demographic data, perform physical examination, conduct laboratory tests (blood, urine, dialysate samples), evaluate peritoneal function, complete SGA scoring, and measure muscle mass.
- Intervention Period:** Conduct biweekly follow-up to record UF volume, AEs and assess medication compliance. Perform serum Alb testing and AE review at the 3-month follow-up.
- 6-Month Post-Intervention:** Repeat all baseline assessments to measure outcome indicators.
- Withdrawal Visit:** Complete safety assessments and data supplementation for participants who withdraw from the study.

7. Statistical Analysis Plan

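### Metabolic acidosis is named as a harm to manage and record, but the only laboratory test scheduled between baseline and month 6 is serum albumin at month 3

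*Protocol*

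**What the plan says.** Three parts of the protocol bear on this point.

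- **The harm.** Section 4.2 holds the dose at 2 L once daily for 6 months "unless safety issues arise (e.g., severe metabolic acidosis), which will be managed with oral sodium bicarbonate as clinically indicated". This is the only safety issue that the dosing section names. Section 5.3 includes the same harm in its list of adverse events: "metabolic acidosis, etc.; recorded throughout the study period". Section 1.2 makes short-term safety a secondary objective.
- **The on-treatment schedule.** Section 6.2 reads: "Conduct biweekly follow-up to record UF volume, AEs and assess medication compliance. Perform serum Alb testing and AE review at the 3-month follow-up". The timeline in 6.1 agrees: "conduct biweekly follow-up (record UF and AEs), perform 3-month serum albumin testing".
- **The panels at either end.** Baseline is to "conduct laboratory tests (blood, urine, dialysate samples"), with no analytes listed. Month 6 is to "Repeat all baseline assessments to measure outcome indicators". Participants who leave early have a withdrawal visit: "Complete safety assessments and data supplementation for participants who withdraw from the study". These safety assessments are not itemised either.

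Serum bicarbonate, total CO2, pH and blood gas are not named at any visit.

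**The concern.** The protocol picks out one metabolic harm in advance and gives a remedy for it, but the on-treatment schedule includes no measurement that would show it. A two-weekly enquiry about adverse events suits harms that a participant can feel or see, such as abdominal distension or diarrhoea. It does not reliably find acidosis that causes no symptoms.

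What is at stake is the safety result. If few cases are recorded, the reader cannot tell whether few occurred or few were looked for. Tests prompted by symptoms or by routine care would also differ from one participant to the next. There is a patient-safety side as well: a scheduled mid-treatment value would let the investigator see a fall in bicarbonate before the 6-month course is over.

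**Working it through.** The protocol gives no figure on this point to reproduce, so the check is a listing of the schedule followed by simple counts.

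**Step 1. Scheduled contacts and what each one measures (sections 5.1, 5.2, 6.1, 6.2).**

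| Time | Scheduled content | Laboratory test | Acid-base test |
|---|---|---|---|
| Baseline | Full assessment | Blood, urine and dialysate, not itemised | Possible, not named |
| Every 2 weeks | Ultrafiltration, adverse events, compliance | None | None |
| Month 3 | Albumin, adverse event review | Serum albumin | None |
| Month 6 | Repeat of baseline | As baseline | Possible, not named |
| Withdrawal visit (leavers only) | Safety assessments, not itemised | Not stated | Possible, not named |

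The albumin time points in 5.1 ("Measured at baseline (enrollment day), 3 months, and 6 months post-intervention") match this table. For a participant who stays in the study, the laboratory tests scheduled after baseline and before month 6 number 1, and the acid-base tests among them number 0.

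**Step 2. What the open panels can and cannot show.** The month-3 test is fixed to a single analyte, so bicarbonate is outside it as written. The baseline and month-6 panels are left open, so not naming bicarbonate there does not show that it is not measured. The gap that the text establishes is therefore the one between those two visits.

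**Step 3. Longest interval between scheduled acid-base tests.** Assumption: the baseline and month-6 panels include bicarbonate.

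- As written: 6 − 0 = 6 months.
- With a month-3 test: max(3 − 0, 6 − 3) = 3 months.

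If the panels do not include it, no scheduled test exists at any point. The documents do not settle which case applies.

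**Step 4. Added assays, with 50 participants (section 2).**

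- Month 3 only: 50 × 1 = 50 at most.
- All three time points, if the panels lack it: 50 × 3 = 150 at most.

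Both are upper limits. The 15% withdrawal allowed for in 7.5 would lower them.

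**Step 5. Size of the undercount.** This would need the rate of acidosis on this solution, the share of cases without symptoms, and the frequency of unscheduled testing. The documents give none of these, so no estimate is offered.

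**The case against.** The strongest reply is that nothing here contradicts anything else. Sections 4.2 and 5.3 do not promise laboratory surveillance. They say that severe acidosis will be treated on clinical indication and that adverse events will be recorded. Taking 6 months as 26 weeks, two-weekly follow-up gives about 26 / 2 = 13 contacts, and each is an occasion to ask and, if need be, to test. Section 5.3 sits under the outcome measures, so the month-6 repeat of baseline assessments can fairly be read as covering safety too. The trial also has no comparator, so an acidosis rate would be hard to attribute to the solution even with more testing.

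Much of this stands, and it rules out several stronger readings:

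- A reader might infer that the trial never measures bicarbonate. The open panels do not support that.
- A reader might infer that treatment of severe acidosis would be delayed to month 6. That would need a case that is severe, lasting and unnoticed through about 13 contacts, and the documents give no ground for expecting one.
- A reader might infer that 4.2 is defective for lacking a bicarbonate threshold. It leaves that decision to clinical judgement, which is a permissible choice.

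The reply does not remove the narrower point. The clinical-indication wording in 4.2 governs bicarbonate treatment and schedules no test. Routine dialysis care may supply values, but the protocol does not say so. The schedule is stated positively, down to the one analyte at month 3, and a visit laboratory schedule is protocol content that would not normally be left to a statistical analysis plan. The lack of a comparator limits attribution, but it is no reason to leave the count itself dependent on chance testing.

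**Conclusion.** The point holds as a cheap improvement to the safety schedule; it is not an internal contradiction. Between baseline and month 6 the protocol schedules no acid-base test, although it names metabolic acidosis as a harm to manage and to record throughout. Acidosis without symptoms in that window would come to light only through an unscheduled test, and a low recorded rate would be hard to interpret.

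The scheduled gap is 6 months if the baseline and month-6 panels include bicarbonate, which is an assumption. Symptomatic or severe cases may well be detected at the two-weekly contacts. The consequence is confined to the short-term safety objective and to patient monitoring; the albumin analysis does not depend on it.

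**What to change.** In 6.1 and 6.2, add serum bicarbonate (or total CO2) to the month-3 albumin sample. Confirm that it is in the baseline and month-6 blood panels, and name it there, so that each participant's change from baseline can be read.

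No new visit or blood draw is needed. The cost is the assays counted above (at most 50, or 150 if the panels lack the test) and an amendment, since section 9 records ethics approval. The recorded acidosis rate may rise because more cases are looked for, and the report should say so. Month-3 values cannot be recovered for participants already past that visit, so an early change is worth more; recruitment is planned to run to June 2027.

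A month-3 test leaves the first weeks of treatment only partly covered: a case beginning soon after enrolment could still wait up to 3 months for a scheduled value. Closing that gap would take an additional early sample, at the cost of a blood draw that the schedule does not now contain.

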4.3 Concomitant Medications

- Participants must maintain stable doses of medications affecting protein metabolism and nutritional supplements throughout the study period.
- Any necessary dose adjustments due to severe clinical complications (e.g., severe infection) will result in participant withdrawal, with follow-up until symptoms stabilize.

5. Outcome Measures

5.1 Primary Outcome Measure

Serum albumin (Alb) level: Measured at baseline (enrollment day), 3 months, and 6 months post-intervention.

5.2 Secondary Outcome Measures

Category	Indicators	Assessment Time Points
Nutritional Status	Prealbumin (PA), Subjective Global Assessment (SGA) score, Transferrin (TF), Lean Body Mass (LBM), Grip strength, Mid-Arm Muscle Circumference (MAMC), Blood amino acid profile	Baseline, 6 months post-intervention
Dialysis Adequacy	Total Kt/Vurea, Peritoneal Creatinine Clearance (Ccr)	Baseline, 6 months post-intervention
Peritoneal Transport Function	Creatinine Mass Transfer Area Coefficient (MTACcr), Dialysate Urea-Creatinine Ratio (R-Ccr)	Baseline, 6 months post-intervention
Dialysis-Related	Ultrafiltration Volume (UF)	Every 2 weeks during intervention

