1.2 Secondary Objectives

- Observe the effects of the solution on dialysis adequacy and peritoneal transport function.
- Monitor adverse events and complications to assess the short-term safety of the solution.

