1.3 Exploratory Objective

To explore the mechanism by which Amino Acid (15) Peritoneal Dialysis Solution improves nutritional status in peritoneal dialysis patients through intra-abdominal amino acid supplementation.

2. Study Design

- **Study Type:** Interventional clinical study
- **Design:** Single-center, prospective, open-label, self-controlled (before-and-after comparison)

- **Total Study Duration:** 24 months (from study initiation to final report completion)
- **Intervention Period per Participant:** 6 months (starting on the enrollment day)
- **Sample Size:** 50 participants

3. Study Population

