3.1 Inclusion Criteria

- Aged \geq 18 years.
- Receiving peritoneal dialysis for \geq 6 months.
- Serum albumin level $<$ 38 g/L.
- No history of peritonitis in the past 3 months and no hospitalization in the past 1 month.
- No severe heart, liver, or other organ dysfunction, or malignant tumors.
- Expected survival time $>$ 1 year.
- Good compliance and willingness to sign the informed consent form.
- Diagnosed with end-stage renal disease (ESRD) with estimated glomerular filtration rate (eGFR) $<$ 15 mL/ (min \cdot 1.73 m 2).

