7.4 Inferential Statistics

- **Primary Outcome:** Compare serum Alb levels before and after intervention using paired t-tests (if normally distributed) or Wilcoxon signed-rank tests (if non-normally distributed).
- **Secondary Outcomes:** Use the same statistical methods as the primary outcome for continuous indicators; use Chi-square tests or Fisher's exact tests for categorical safety indicators.
- **Correlation Analysis:** Use Pearson or Spearman correlation tests to explore associations between nutritional indicators and other outcomes.
- **Significance Level:** Two-tailed $\alpha = 0.05$.

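### One of the two adequacy outcomes, total Kt/Vurea, includes kidney clearance, so loss of residual kidney function over six months can be read as an effect of the solution

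*Protocol*

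**What the plan says.** The secondary objective in Protocol section 1.2 is to "Observe the effects of the solution on dialysis adequacy and peritoneal transport function". Section 5.2 serves the adequacy part with two indicators, "Total Kt/Vurea, Peritoneal Creatinine Clearance (Ccr"), each taken at baseline and at 6 months. Kt/Vurea is specified as the total, creatinine clearance as the peritoneal part.

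The design in section 2 is "Single-center, prospective, open-label, self-controlled (before-and-after comparison"). Section 4.2 sets out "Continuous intervention for 6 months per participant" and adds "Participants maintain their original peritoneal dialysis regimen throughout the study", apart from the daily exchange of one glucose bag for the study solution.

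On kidney function at entry, section 3.1 asks only for this: "Diagnosed with end-stage renal disease (ESRD) with estimated glomerular filtration rate (eGFR") below 15 mL/min per 1.73 m². Sections 3.1 to 3.3 contain no anuria requirement, urine-volume limit or condition that residual function be stable.

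For secondary outcomes, section 7.4 says: "Use the same statistical methods as the primary outcome for continuous indicators". That means a paired t-test or Wilcoxon signed-rank test, with no adjustment named. Section 6.2 has the baseline visit "conduct laboratory tests (blood, urine, dialysate samples), evaluate peritoneal function", and all baseline assessments are repeated at 6 months. Renal Kt/V, peritoneal Kt/V, urine volume and residual kidney function do not appear as outcomes.

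**The concern.** The solution goes into the peritoneal cavity, so its direct effect on urea removal is on the peritoneal component. Total Kt/Vurea also contains a renal component, which can fall over six months as the underlying disease progresses. With a control arm that trend would be shared by both groups and would cancel in the comparison. Here nothing cancels it, and the paired test sees only the sum.

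Two wrong readings are possible. A fall in total Kt/Vurea caused by the kidneys may be reported as the solution reducing adequacy. A real peritoneal gain may be offset by renal loss and reported as no change. The second adequacy indicator does not share the problem, so the two could disagree for a reason unrelated to the product, and the protocol does not say how such a disagreement would be read.

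**Working it through.** **The plan's own figure.** The protocol gives no figure for Kt/Vurea: no standard deviation, residual clearance, rate of loss or target difference. Its only sample-size calculation is for albumin (section 7.5: SD of change 4 g/L, difference 3 g/L, two-sided 5%, power 80%). The normal approximation gives ((1.960 + 0.842) × 4/3)² = 13.95, rounded up to 14, which reproduces the stated minimum. The present point does not touch that figure.

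**Decomposition.** By definition:

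- total Kt/V = peritoneal Kt/V + renal Kt/V
- change in total = change in peritoneal + change in renal

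The paired test in section 7.4 estimates the left side. The objective concerns the solution, which acts on the first term on the right. The second term is the bias.

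**Size of the renal term.** The urea distribution volume V is an assumption (35 L, range 30 to 40 L), as is the mean loss of renal urea clearance (0.25 to 1 mL/min over six months).

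- 1 mL/min = 1.44 L/day = 10.08 L/week
- Fall in weekly Kt/V = 10.08 × loss in mL/min ÷ V

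| Mean loss (mL/min) | V = 40 L | V = 35 L | V = 30 L |
|---|---|---|---|
| 0.25 | 0.063 | 0.072 | 0.084 |
| 0.5 | 0.126 | 0.144 | 0.168 |
| 1 | 0.252 | 0.288 | 0.336 |

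The loss is the mean over all participants, and anuric participants contribute zero. If, say, half were anuric, a loss of 1 mL/min in the others would be a cohort mean of 0.5 mL/min.

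**What the planned test would do.** Suppose the solution has no effect and renal Kt/V falls by a given mean amount. The probability that the two-sided 5% paired t-test calls the change in total Kt/Vurea significant follows from the noncentral t distribution with noncentrality (mean fall ÷ SD of change) × √N. The SDs are assumed. N = 50 is full enrolment; N = 42 is the approximate number of completers at 15% withdrawal (50 × 0.85 = 42.5).

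| SD of change | N | Fall 0.05 | Fall 0.10 | Fall 0.15 | Fall 0.20 |
|---|---|---|---|---|---|
| 0.2 | 50 | 41% | 93% | >99% | >99% |
| 0.3 | 50 | 21% | 64% | 93% | >99% |
| 0.4 | 50 | 14% | 41% | 74% | 93% |
| 0.3 | 42 | 18% | 56% | 89% | 99% |

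With no renal drift the rate is the nominal 5%. Under these assumptions, a mean fall of about 0.41 SD of the change (0.45 SD at 42 completers) is enough for an 80% chance of a significant result with no solution effect.

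**Direction.** Renal loss makes the second term negative. It can produce an apparent fall or hide a gain, but it cannot produce an apparent rise.

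**The case against.** Several objections carry weight.

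- **Adequacy does not rest on total Kt/Vurea alone.** A reader might infer that the adequacy objective cannot be answered at all. Section 5.2 does not support that: peritoneal creatinine clearance excludes the kidney and is free of this bias, and the creatinine mass transfer coefficient and ultrafiltration volume are recorded too. What is missing is a peritoneal measure for urea.
- **Total Kt/Vurea is a legitimate description of the clearance a patient receives.** This stands, and it is a reason to keep reporting it. It is not a reason to use its before-after change as the test of the solution. No section says outright that a change will be credited to the solution regardless of kidney function, but the objective together with the planned test leads there.
- **The bias may be small or absent.** This stands as to size. All patients have had at least six months of dialysis, and the documents do not say how many still pass urine. Nothing restricts entry to anuric patients, however, and urine is to be collected.
- **A reader might infer that kidney loss would swamp any solution effect.** The documents cannot support such a ratio. Assume a loss of 1 mL/min and a 0.2 L change in the swapped bag's drained volume at a dialysate-to-plasma urea ratio of 0.9: the renal term is 0.288 and the peritoneal term 0.2 × 7 × 0.9 ÷ 35 = 0.036, a ratio of 8. Assume 0.25 mL/min and 0.5 L instead: the terms are 0.072 and 0.090, a ratio of 0.8. V cancels, and neither remaining input is given.
- **Splitting the components could be left to a statistical analysis plan.** Presentation could be. Which quantity is tested for the solution effect is already fixed by sections 5.2 and 7.4.

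**Conclusion.** The point holds for one of two adequacy indicators. Total Kt/Vurea, tested before against after without a control arm or adjustment in patients who need not be anuric, mixes any change in kidney clearance with the effect of the solution. The mixing follows from the definition of the outcome and needs no assumption.

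Its size does rest on assumptions: about 0.07 to 0.29 in weekly Kt/V for a mean loss of 0.25 to 1 mL/min at V = 35 L, and zero if all participants are anuric. Under the assumed SDs of change, a mean fall of 0.10 alone would give a significant result in 41% to 93% of trials of 50.

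The consequence is limited. This is a secondary outcome, the error from kidney loss runs against the product or hides a gain, and the albumin comparison is not affected by this point. It is worth correcting because the planned samples already allow it.

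**What to change.** In section 5.2, make weekly peritoneal Kt/Vurea the urea measure tested for the solution effect, matching the peritoneal creatinine clearance already chosen. Report renal and total Kt/Vurea beside it at baseline and month 6 as descriptive results, and interpret a change in total Kt/Vurea only in the light of its two parts.

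Add one sentence of limitation: this removes drift from residual kidney function only. Peritoneal clearance can also change over six months for reasons other than the solution, and an uncontrolled design cannot separate those time trends.

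The cost is a wording change. Urine and dialysate are already to be collected at baseline and repeated at 6 months, and total Kt/Vurea cannot be calculated without both components, so no further visit or sample is needed.

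### The second peritoneal transport outcome, computed as named, mixes membrane transport with the blood urea-to-creatinine ratio, and its abbreviation does not match its name

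*Protocol*

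**What the plan says.** One secondary objective in Protocol section 1.2 is to "Observe the effects of the solution on dialysis adequacy and peritoneal transport function". The table in section 5.2 serves the transport part with two indicators, each taken at baseline and 6 months: "Creatinine Mass Transfer Area Coefficient (MTACcr") and "Dialysate Urea-Creatinine Ratio (R-Ccr"). The second is named as two solutes in one fluid. No formula for it appears anywhere in the protocol.

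In the row above, under dialysis adequacy, the same table has "Peritoneal Creatinine Clearance (Ccr"), so the letters Ccr already have a meaning there.

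The exposure is set in section 4.2: "Replace one bag of conventional glucose-based dialysis solution with Amino Acid (15) Peritoneal Dialysis Solution after lunch, once daily", for 6 months. Section 1.3 describes the route of action as working "through intra-abdominal amino acid supplementation". Section 2 gives the design as "Single-center, prospective, open-label, self-controlled (before-and-after comparison"), and section 7.4 tests continuous secondary outcomes with a paired t-test or Wilcoxon signed-rank test. Under section 6.2 the baseline visit is to "conduct laboratory tests (blood, urine, dialysate samples") and evaluate peritoneal function, and all baseline assessments are repeated at 6 months.

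**The concern.** A small-solute transport index normally sets dialysate against plasma for the same solute, so that the blood level cancels. A ratio of two different solutes, both measured in dialysate, does not do this: the blood levels of both stay in it.

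That matters here because the intervention can act on one of them. Urea is the end product of amino acid nitrogen, so a daily amino acid dwell may raise blood urea relative to creatinine with no change in the membrane. The planned paired comparison of this indicator would show the resulting shift under the heading of transport function, and nothing in that comparison separates the two sources.

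The label raises a second doubt. A urea-creatinine ratio is not what R-Ccr would abbreviate in a table where Ccr is a creatinine clearance. Name and abbreviation point to different quantities, and no formula decides between them.

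**Working it through.** **Inputs from the protocol.** The indicator's name, its place under transport function and its two time points (5.2); one amino acid bag a day for 6 months (4.2); a paired before/after test (7.4). The protocol gives no expected value for either transport indicator, no nitrogen content for the product and no expected change in urea, so there is no figure of its own to reproduce on this point.

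**Assumed inputs, for illustration only.** Baseline D/P creatinine 0.65; D/P urea 0.90 throughout; plasma creatinine unchanged; a rise in plasma urea of between 5% and 40%.

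**Step 1: the identity.** Let D be a dialysate and P a plasma concentration. Since D = P × (D/P) for each solute,

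D_urea / D_cr = (P_urea / P_cr) × [(D/P)_urea / (D/P)_cr].

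The first factor is the blood ratio. The second carries the transport information.

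**Step 2: transport fixed, blood urea changes.** The second factor stays at 0.90 / 0.65 = 1.385 and cancels from the before/after comparison. The relative change in the indicator is then the relative change in P_urea / P_cr:

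| Assumed rise in plasma urea | Change in dialysate urea/creatinine | Change in D/P creatinine |
|---|---|---|
| 5% | +5% | 0% |
| 10% | +10% | 0% |
| 20% | +20% | 0% |
| 30% | +30% | 0% |
| 40% | +40% | 0% |

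**Step 3: blood urea fixed, transport changes.** Let D/P creatinine rise from 0.65 to 0.75, which is 0.75 / 0.65 − 1 = +15.4%. The indicator changes by 0.65 / 0.75 − 1 = −13.3%. It does respond to transport, and it falls when creatinine transport rises.

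**Step 4: both change.** With the same rise in D/P creatinine:
- plasma urea +15.4%: (0.75 / 0.65) × (0.65 / 0.75) = 1, so the indicator shows no change;
- plasma urea +20%: 1.20 × (0.65 / 0.75) = 1.040, so the indicator rises by 4.0% although the membrane effect alone would lower it by 13.3%.

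**Step 5: the label.** Possible readings of the entry, set side by side:

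| Reading | Consequence |
|---|---|
| Dialysate urea over dialysate creatinine, as named | Confounded by the blood ratio (steps 2 to 4) |
| Dialysate-to-plasma creatinine ratio | A transport index, but not what is written |
| Creatinine clearance | Listed in the wrong row and under the wrong name |
| Ratio of urea to creatinine clearance | Each blood level is divided out, but the text does not say this |

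Every reading calls for a change to the line.

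**The case against.** The strongest reply is that the label is visibly inconsistent, so the intended quantity is unknown and the algebra may be aimed at a misprint. If a D/P creatinine ratio or a ratio of clearances was meant, the objection is to wording only, and an operational formula for a secondary laboratory index could sit in a statistical analysis plan that is not shown. The first part stands: a labelling error is possible. It does not remove the point, because choosing and naming an outcome is the protocol's task, and the outcome as named does not isolate transport.

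Four stronger inferences are tempting, and the documents do not support them.

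- **That the ratio cannot show a transport change at all.** Step 3 shows that it responds. It is confounded, not blind.
- **That the transport objective will be answered wrongly.** The creatinine mass transfer area coefficient stands first in the same row, is planned at both visits, and takes plasma creatinine into account.
- **That the missing control arm is the cause.** If the product itself raises urea, treated and control participants would differ in this ratio for the same non-membrane reason. Nor is the blood shift necessarily hidden: total Kt/Vurea and peritoneal creatinine clearance, also planned at both visits, need blood urea and creatinine, so it could be examined from planned data.
- **That the distortion has a known size.** The 5% to 40% range is assumed, and x% in giving x% out is an identity, not evidence of magnitude. Net anabolism could blunt any urea rise.

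**Conclusion.** The point holds for the outcome as the protocol names it. A before/after change in a dialysate urea/creatinine ratio cannot, taken alone, be attributed to the membrane, because any proportional change in the blood urea/creatinine ratio enters it in full. Under the assumed D/P values, a urea rise of about 15% would conceal a shift in D/P creatinine from 0.65 to 0.75. Whether a rise of that order will occur cannot be judged from the protocol.

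The consequence is limited. This is one of two indicators for part of one secondary objective, the other indicator remains usable, and neither the primary outcome nor the sample size is touched. It is a minor correction, best made before results exist. The algebra needs no assumption beyond computing the ratio as written; its relevance here rests on the amino acid load being able to change blood urea relative to creatinine.

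**What to change.** In the section 5.2 table, replace the second transport indicator with the dialysate-to-plasma creatinine ratio, and state its formula. Measure it at the same dwell time and with the same test solution at baseline and 6 months, so that the before/after comparison is like with like. If a creatinine clearance was meant, rename the entry accordingly and list it under dialysis adequacy. In either case, do not interpret a dialysate urea/creatinine ratio as evidence of a change in transport.

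The cost is small. One table line changes, and blood and dialysate creatinine are already needed at both visits for the mass transfer coefficient and the peritoneal clearance. Section 6.2 says only that peritoneal function is evaluated and names no dwell time or test solution, so a sentence there may be needed as well. The drawback is that the new index partly overlaps with the mass transfer coefficient.
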